#### 4.4.1.2. Data Handling Rules

A sensitivity analysis using multiple imputations will be performed in order to evaluate the impact of missing RT-PCR results on the primary endpoint. RT-PCR results from samples that were out of stability are also considered missing. For ARIs where no RT-PCR result can be linked to the considered ARI episode (based on the rules defined in [Section 4.4.2.1.2](#)), the RT-PCR result (positive or negative) will be imputed using the period the ARI occurred, the geographic location (RSV census regionsa), the age, the risk level of the participants and the severity of the episode as parameters in the model. If a single RT-PCR test is available, no imputation will be performed.

Moreover, the primary analysis model already accounts for drop outs (see [Section 4.4.2.2](#)), since participants follow up time is taken into consideration.

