#### 4.4.1.1.1. Conditional Power

Based on [Figure 1](#) and [Figure 2](#), there are two occasions that the IDMC will require to evaluate the conditional power. For a NH only study or a NH and SH study, the conditional power is required if at the end of the respective RSV seasons the incidence is exceptionally low (less than 18 observed RT-PCR-confirmed RSV-mediated lower respiratory tract disease (LRTD) events per Case Definition #2, based on the PPE set) and the interim analysis is negative.

The conditional power is calculated as follows:

1. Calculate the significance level at the IA,  $\alpha'$ .
  - Study only performed in the Northern Hemisphere: See *'The Interim Analysis will be conducted by the IDMC'* part in [Table 4](#). Use the significance level resulting from [Table 4](#), step 4 in the corresponding cell.
  - Study performed in the Northern and Southern Hemisphere: see *'If Interim Analysis 1 is negative and at the end of the SH RSV season < 18 events\* are observed a second interim analysis will be conducted (potentially 3 analyses will be performed)'* part in [Table 5](#). Use the significance level resulting from [Table 5](#), step 2 in the corresponding cell.
2. Simulate the number of Case definitions #2 expected at the end of the Season 2, 20000 simulations, assuming 900 additional participants per group (1000 per group assuming a 10% drop out rate), a 0.75% RSV incidence and an expected 70% VE.
3. For each of the 20000 simulations, calculate the adjusted significance level used for the final analysis and use an exact Poisson regression to compare active and placebo:
  - a. Calculate total number of events observed until the end of the second RSV season (x observed at the time of the interim analysis, n number of events simulated for the second season) for each simulation. Total number of events throughout is  $x + n$
  - b. The corrected IF of the interim analysis and the final analysis is  $(x / (x + n), 1)$ .
  - c. Given the  $\alpha'$  already spent in the interim analysis, the remaining alpha will be spent using a user defined alpha spending function approach based on  $\alpha'$  that was already spent and the corrected IF. This will be  $\alpha''$ . Note: for each simulation  $\alpha''$  will be slightly different.

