#### 4.4.2.2. Analysis Methods

For each of the 3 primary endpoints the following will be performed: an exact Poisson regression will be fitted with the event rate, defined as the number of cases over the follow-up time (offset) as dependent variable and the vaccination group and age and being at increased risk for severe RSV disease (both as stratified) as independent variables. For cases, the follow-up time is defined as the time between vaccination and the occurrence of the first event (according to the considered endpoint), for non-cases, it is the time between vaccination and the end of season visit. In case the EOS visit is missing then the 15th of May 2020 will be used. However, for participants that discontinued before the end of the season and had an event (according to the considered endpoint), the follow-up time is defined as the time between vaccination and the occurrence of the first event and for participants that discontinued before having an event, follow-up time is the time between vaccination and the date of last contact (date of discontinuation).

Note: in case more than one end of season visits are available, the latest will be used to determine the follow up time.

Thus, all participants are included in the analysis according to their follow-up time. The exact one sided p-value corresponding to vaccination group will be compared with the one sided cut-off as described above (Section 4.4.1.1).

If the p-value is below the cut-off for at least 1 of the 3 primary endpoints, proof of concept is demonstrated. The individual exact 2-sided CIs ( $1-2 \times$  cut-off) for the VE (1-relative risk rate), measured by each of the 3 endpoints, will be calculated from the regression model described above and graphically depicted with forest plots.

The primary analysis will be performed on the PPE population, which will take cases into account with an onset at least 14 days after vaccination.

As sensitivity analyses the above Poisson model will be repeated similar to the primary analysis:

- based on the FAS (which also does not take into account the restriction on the onset [at least 14 days] and will count cases from vaccination on Day 1 onwards). RT-PCR results from samples that were out of stability, but tested RSV positive are taken into account in this analysis.
- based on the PPE set but taking into account only RT-PCR test results from the central laboratory (i.e., excluding the local test results for hospitalized participants)

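### The imputation model for missing RT-PCR results omits vaccination group, so the one analysis that imputes them understates VE when the vaccine works

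*SAP*

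**What the plan says.** Section 4.4.1.2 sets up the analysis "in order to evaluate the impact of missing RT-PCR results on the primary endpoint". For an ARI to which no result can be linked, "the RT-PCR result (positive or negative) will be imputed using the period the ARI occurred, the geographic location" (RSV census region), "the age, the risk level of the participants and the severity of the episode as parameters in the model". The list is closed: five predictors, with no wording that leaves room for more. The same section adds that "RT-PCR results from samples that were out of stability are also considered missing", and that nothing is imputed once any single test result is available.

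The model applied to the primary endpoints in Section 4.4.2.2 is an exact Poisson regression with "the vaccination group and age and being at increased risk for severe RSV disease (both as stratified) as independent variables". VE is read from the vaccination-group term.

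Two neighbouring provisions touch missing data. Dropout is left to follow-up time: "the primary analysis model already accounts for drop outs". The FAS sensitivity analysis in Section 4.4.2.2 restores some results: "RT-PCR results from samples that were out of stability, but tested RSV positive are taken into account in this analysis". It does nothing for an ARI with no result at all.

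**The concern.** If the vaccine prevents RSV disease, an ARI in a vaccinated participant is less likely to be RSV-positive than one in a placebo participant. A model without vaccination group gives both the same probability once period, region, age, risk level and severity match. Imputed cases then fall almost evenly on the two arms, while observed cases do not. The imputation model lacks the very term that the analysis model is meant to estimate.

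More imputations do not remove the resulting attenuation, and it appears even when results are missing completely at random. A reader who sees VE fall in this analysis would blame the missing results, when some or all of the fall comes from the imputation model.

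**Working it through.** **Inputs from the SAP.** Section 4.4.1.1.1 plans by "assuming 900 additional participants per group (1000 per group assuming a 10% drop out rate), a 0.75% RSV incidence and an expected 70% VE", for Case Definition 2. Section 1.2 gives 2,900 participants per arm.

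**Assumptions, not in the SAP.** The share *m* of ARIs with no usable result, missing at random at the same rate in both arms. The number *k* of non-RSV ARIs per placebo RSV case, equal in both arms. Only ARIs that meet the symptom criteria can become endpoint cases, so *k* refers to those.

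**Check on the inputs.** The SAP gives no figure for the imputation analysis. It does expect 9 extra events if the study is expanded (Table 4). With 900 per arm: 900 × 0.0075 + 900 × 0.0075 × 0.30 = 6.75 + 2.025 = 8.775, which rounds to 9. So 0.75% is the placebo incidence, and the inputs are read as the SAP uses them.

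**One case in full.** Take 2,900 per arm and an assumed 10% non-RSV ARI rate (290 per arm, *k* = 290/21.75 = 13.3).

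- RSV cases: placebo 2,900 × 0.0075 = 21.75; vaccine 21.75 × 0.30 = 6.525.
- Arm-pooled positivity: 28.275 / (28.275 + 580) = 28.275 / 608.275 = 4.65%.
- At 10% missing, placebo: 0.9 × 21.75 + 0.1 × 311.75 × 0.0465 = 21.02.
- At 10% missing, vaccine: 0.9 × 6.525 + 0.1 × 296.525 × 0.0465 = 7.25.
- VE = 1 − 7.25/21.02 = 65.5%, against a true 70%.

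With positivity taken by arm, the placebo count is 0.9 × 21.75 + 0.1 × 311.75 × (21.75/311.75) = 21.75. The vaccine count is 6.525 in the same way, so VE is 70%. The primary rule (no confirmation, no case) also gives 70%: 1 − (0.9 × 6.525)/(0.9 × 21.75).

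**General form.** Incidence and sample size cancel:

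π = (2 − VE) / [(2 − VE) + 2k]

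VE_MI = 1 − [(1 − m)(1 − VE) + m(1 − VE + k)π] / [(1 − m) + m(1 + k)π]

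Expected VE (%) when true VE is 70%:

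| Missing | k = 2 | k = 5 | k = 10 | k = 20 |
|---|---|---|---|---|
| 2% | 69.3 | 69.2 | 69.1 | 69.1 |
| 5% | 68.3 | 68.0 | 67.8 | 67.8 |
| 10% | 66.5 | 65.8 | 65.6 | 65.4 |
| 20% | 62.7 | 61.4 | 60.9 | 60.5 |
| 30% | 58.8 | 56.7 | 55.8 | 55.3 |

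With true VE of 50% and *k* = 10, the column reads 49.3, 48.2, 46.4, 42.7 and 38.8. With true VE of 0, every entry is 0.

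**Where the pull leads.** As *m* approaches 1 the expression tends to 1 − (1 − VE + k)/(1 + k) = VE/(1 + k). That is the arm ratio of the untested ARIs: 0.7/3 = 23% for *k* = 2, but 0.7/11 = 6% for *k* = 10.

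**Does severity stand in for group?** A large simulation put severity and period in a logistic imputation model (10% non-RSV ARI rate; RSV episodes more often severe and more often in the peak period). One scenario also had the vaccine reduce severity. Without group, VE was 67.4-68.1% at 5% missing, 65.1% at 10%, 59.9-61.3% at 20% and 55.9-56.8% at 30%. With group it was 69.0-70.8% throughout. At true VE of 0, the two versions differed by at most 0.7 points.

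**The case against.** The strongest reply is that little hangs on this. Proof of concept rests on the primary exact Poisson p-values, and no imputed result enters them. At VE = 0 the omission causes no shift, and with a working vaccine the error is downward, so it cannot manufacture efficacy. All of that stands. A reader might infer that the primary result or the type I error is compromised; the SAP does not support that reading.

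Missingness may also be low. Imputation applies only when no result at all can be linked. One positive swab or sputum sample is enough for confirmation, and a local hospital result can replace a missing central one (Section 4.4.2.1.2). At 2-5% missing the shift is about 1-2 points. For comparison, 7 versus 22 cases gives an exact 95% CI for VE of roughly 23% to 89%. This stands too: the 20% and 30% rows are illustrations, and nothing in the SAP says that they will occur.

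It could be called the only missing-data sensitivity analysis, but that is too broad. The FAS analysis brings back out-of-stability samples that tested positive. The imputation is the only analysis that fills in missing RT-PCR results.

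Finally, leaving group out can be a deliberate conservative choice. It can, but the SAP does not present it as one, and severity does not make up for the missing term.

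**Conclusion.** The point holds as a specification error in a supportive analysis; it should be fixed, but it is not critical. Whenever true VE is not 0, the stated model biases the imputed VE toward the arm ratio of the untested ARIs. That target is close to, but not exactly, VE = 0, and only if most untested ARIs are non-RSV.

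With true VE of 70%, the loss is about 1 point at 2% missing, 2 at 5%, 3.5-4.6 at 10%, 7-10 at 20% and 11-15 at 30%. These figures assume results missing at random, equal non-RSV ARI rates in the arms and *k* between 2 and 20. The direction is much less sensitive to *k* than the size is to the missing share, which the SAP does not report. Under the same conditions the primary rule is unbiased, so the sensitivity analysis is more biased than the analysis it checks.

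**What to change.** In Section 4.4.1.2, add vaccination group to the predictors, or state that imputation is done separately by arm. If the arm-pooled model is kept, label it as a conservative analysis that assumes no vaccine effect among ARIs with missing results, and report the version with group beside it. State the share of ARIs imputed, by arm, so that a reader can judge the size.

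The cost is one model term and a rerun on data already held. It is not purely a text change, though. Section 1.6 of this amendment speaks of the first-season primary analysis in the past tense, and the later-season sensitivity analyses in Section 5.4.1.2 do not include imputation. If the first-season analysis has been run, first check whether the code already contained group. If it did not, relabel the existing output and mark the added version post hoc if it is run after unblinding.

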#### 4.4.2. Primary Efficacy Endpoints

##### 4.4.2.1. Definition

The three primary efficacy endpoints are first occurrence of RT-PCR confirmed RSV-mediated LRTD according to each of the 3 case definitions shown in [Table 6](#):

**Table 6: Case Definitions**

Case Definition #1	Case Definition #2	Case Definition #3
≥3 symptoms of LRTI (new onset or worsening)	≥2 symptoms of LRTI (new onset or worsening)	≥2 symptoms of LRTI, OR ≥1 symptom of LRTI combined with ≥1 systemic symptom (new onset or worsening)
RT-PCR confirmation of RSV		

LRTI = lower respiratory tract infection

To meet the primary endpoint criteria for a case definition, the following criteria need to be fulfilled:

a <https://www.cdc.gov/surveillance/nrevss/rsv/region.html>

- The participant must show the necessary number of signs and symptoms (new onset or worsening) according to the considered case definition. Which symptoms will be taken into account and how the number of symptoms will be counted is defined in Section 4.4.2.1.1.
- The considered ARI episode must be RT-PCR confirmed for RSV. RSV RT-PCR confirmation is defined in Section 4.4.2.1.2.

First occurrence of a considered endpoint is defined as the first day of symptoms of the first RSV-confirmed ARI episode where the criteria for the respective case definition are fulfilled on at least one assessment of the considered episode. Only episodes occurring in the first season of the participant are taken into account for the primary analysis.

#### 4.4.2.1.1. Counting Symptoms

During an ARI episode, the participant is asked to daily report symptoms (RiiQ Symptom Scale) and body temperature on the participants device (eDiary). In addition, during the ARI day 3-5 clinical visit, the subject must report symptoms (RiiQ Symptom Scale) and body temperature on the sites device (eDevice) and a clinical assessment is performed by the study staff. In the remainder of the text, assessment will refer to any of the following: to the patient reported outcome on the participants eDiary, to the participant reported outcome on the sites eDevice or to the clinical assessment.

Table 7 shows the LRTI and systemic signs and symptoms that are taken into account for the case definitions and what the corresponding terms are in the RiiQ and the clinical assessment.

**Table 7: Symptoms of Lower Respiratory Tract Infection and Systemic Symptoms as per RiiQ or Clinical Assessment**

	Symptoms from Case Definition	RiiQ Term	Clinical Assessment Term (ARI Days 3-5 Clinical Visit)
Symptoms of LRTI	Cough	Cough	Cough
	Shortness of breath	Short of breath	Dyspnea or decreased oxygen saturation
	Sputum production	Coughing up phlegm (sputum)	Sputum production
	Wheezing	Wheezing	Wheezing or rhonchi, rales or other sign of consolidation
	Tachypnea		Tachypnea
Systemic Symptoms	Fatigue	Fatigue (tiredness)	Malaise (tiredness)
	Fever		Fever
	Feverishness	Feeling feverish or Fever*	

LRTI =lower respiratory tract infection, RiiQ = Respiratory Infection Intensity and Impact Questionnaire

\* Fever defined based on the daily temperature reported from the participants in the eDiary

#### **New onset or worsening of symptoms:**

To determine new onset or worsening of symptoms, symptoms should be compared with the respective baseline of the season wherein the episode started:

- Clinical assessment by the site staff will be compared with clinical assessment baseline by the site staff.
- Patient reported outcomes reported on the site's eDevice and on the participants eDiary will be compared with the baseline patient reported outcomes.

Symptoms present during an ARI episode but not at the baseline assessment will be considered as symptoms with a new onset. Symptoms present at the baseline assessment that become worse (higher severity) during the ARI episode will be considered as worsening symptoms.

For assessments that are numerically scored (Decreased oxygen, tachypnea, and fever) new onset or worsening is defined as follows:

- Decreased oxygen saturation is defined as:
  - oxygen saturation of  $<90\%$  for participants with a baseline oxygen saturation of  $\geq 90\%$  or a missing baseline at randomization (new onset)
  - for participants with baseline oxygen saturation  $<90\%$ , decreased oxygen saturation is defined as a  $\geq 3\%$  decrease in their oxygen saturation from baseline (worsening).
- Tachypnea is defined by respiratory rate (RR)  $>20$  breaths per minute:
  - For subjects with baseline RR  $\leq 20$  or a missing baseline, a value  $>20$  is considered a new onset.
  - For subjects with baseline RR  $>20$  (and  $\leq 25$ ), a value  $>25$  is considered a worsening.
- Fever: all temperatures  $>37.8^{\circ}\text{C}$  during an ARI episode will be considered as a fever, regardless of the baseline temperature of the participant. For example, if a subject has baseline temperature of 37.9 degrees Celsius and during the ARI episode his temperature of is again 37.9 degrees Celsius, it will be counted as a systemic symptom of fever.

Note 1: Shortness of breath and respiratory effort reported at the clinical assessment form will not be taken into account for the case definitions.

Note 2: If a participant at the clinical assessment reported a new onset or worsening of dyspnea and had decreased oxygen saturation, then it counts only as one symptom towards the case definitions. Similarly, if a participant had a new onset or worsening of wheezing and rhonchi, rales or other sign of consolidation, it also counts as one symptom.

Note 3: Example of selecting the baseline of the season in which the ARI started: if an ARI episode starts in Season 2 and continues during Season 3, then all assessments related to that ARI episode will be evaluated in comparison to the Day 365 baseline to determine new onset or worsening.

Missing baseline assessments will not be imputed, in case of missing baseline symptoms the participant will be considered to have no baseline symptoms at all.

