## **2. GENERAL ANALYSIS DEFINITIONS**

### **2.1. Study Phases**

A baseline (or reference) value for safety and immunogenicity will be defined as the value of the last available assessment prior to the first vaccination on Day 1. If there was no immunogenicity assessment done pre-vaccination, the assessment post-vaccination on Day 1 can be used as the baseline value for the immunogenicity analysis, if available.

A baseline (or reference) value for the efficacy analysis of the first RSV season will be defined as the worst value of the available assessment at Day 1 visit, if Day 1 visit is not available the Day 1 unscheduled visit closest to the day of vaccination will be used. In case two or more assessments are available at the same visit or at the same day of the selected baseline visit (for example assessments both at the eDiary and eDevice) the worst will be used (per question).

A new baseline (or reference) value for the efficacy analysis of the second and third RSV season will be defined as the worst value of the available assessment at Day 365/Day 730 visit, if Day 365/Day 730 visit is not available the Day 365/Day 730 unscheduled visit closest to the relative day 365/day 730 will be used. In case no Day 365/Day 730 visit (schedule or unscheduled) is available then the baseline of the first/second (or first) RSV season will be used. In case two or more assessments are available at the same visit or at the same day of the selected baseline visit (for example assessments both at the eDiary and eDevice) the worst value will be used (per question).

The safety analysis will present all results by period, unless specified otherwise. Immunogenicity results will be presented per analysis time point (see Section 2.1.2) as appropriate. Listings will be shown per phase, period and time point. Efficacy results will be presented across the entire season or per timepoint, where appropriate.

Study day or relative day is defined as follows:

Study Day = visit date - date of Day 1 + 1; if visit date > date of Day 1 (date of first vaccination).

Study Day = visit date - date of Day 1; if visit date < date of Day 1 (date of first vaccination).

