### 5.4. Efficacy Analysis

#### 5.4.1. Exploratory Efficacy Variable(s)

##### 5.4.1.1. Definition

Other exploratory efficacy endpoints are:

- **First occurrence of RT-PCR-confirmed RSV-mediated LRTD during the second RSV season and during the third RSV season according to Case Definition 1**

This is defined similarly as the primary endpoint, but only counted in the respective RSV season. The baseline assessment for the second RSV season is the Day 365 (Month 12) visit and for the third RSV season it is the Day 730 (Month 24) visit (see Section 2.1). New onset or worsening is defined similarly as for the primary endpoint, by comparing symptoms occurring during the ARI episode to symptoms reported at the new baseline (instead of by comparing to Day 1). First occurrence of a considered endpoint during the second or third RSV season is defined as the first episode of the considered endpoint in a given RSV season (regardless A or B strain, unless otherwise specified).

- **First occurrence of RT-PCR-confirmed RSV-mediated LRTD over season two and three and over all three RSV seasons according Case Definition 1**

This is defined similarly as the primary endpoint but taking into account events over season two and three and over all three seasons. The baseline assessment for the second RSV season is the Day 365 (Month 12) visit and for the third RSV season it is the Day 730 (Month 24) visit (see Section 2.1). New onset or worsening is defined similarly as for the primary endpoint, by comparing symptoms occurring during the ARI episode to symptoms reported at the new baseline (instead of comparing to Day 1). When evaluating the vaccine efficacy over season two and three or over all three seasons, first occurrence of a considered endpoint over two or three seasons is defined as the first episode over the two or three periods (regardless A or B strain, unless otherwise specified).

The following exploratory efficacy endpoints, are defined similarly as the corresponding endpoints during the first RSV season (see Section 4.4.3 and 4.4.4), but baseline, new onset or worsening and first occurrence are defined the same way as for RT-PCR-confirmed RSV-mediated LRTD, during the second and third RSV season and over season two and three or over all three RSV seasons. These endpoints might also be explored during the second or third RSV season and across season two and three or across all three RSV seasons.

- **First occurrence of any RT-PCR-confirmed RSV ARI**

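### In Seasons 2 and 3, a participant who attends Day 365/730 without the symptom assessment is scored as symptom-free, although an earlier-season baseline exists

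*SAP*

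**What the plan says.** Three places in the SAP decide what a Season 2 or 3 symptom is compared with.

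- **Section 2.1 (Study Phases)** defines the baseline for these seasons. It "will be defined as the worst value of the available assessment at Day 365/Day 730 visit", or at the nearest unscheduled visit if the scheduled one is absent. Then: "In case no Day 365/Day 730 visit (schedule or unscheduled) is available then the baseline of the first/second (or first) RSV season will be used". The trigger for that fallback is the absence of a visit.
- **Section 4.4.2.1.1 (Counting Symptoms)** gives the rule for missing data: "Missing baseline assessments will not be imputed, in case of missing baseline symptoms the participant will be considered to have no baseline symptoms". The trigger here is a missing assessment or symptom. The section is not confined to Season 1. It says "symptoms should be compared with the respective baseline of the season wherein the episode started", and Note 3, directly before the missing-baseline sentence, uses a Season 2 episode for which "all assessments related to that ARI episode will be evaluated in comparison to the Day 365 baseline to determine new onset or worsening".
- **Section 5.4.1.1** defines the Season 2, Season 3 and combined-season endpoints. It points to Section 2.1 for the baseline and to the primary endpoint for the comparison: "New onset or worsening is defined similarly as for the primary endpoint, by comparing symptoms occurring during the ARI episode to symptoms reported at the". The sentence goes on to name the season's own baseline in place of Day 1.

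Section 5.4.1.2 keeps participants without a Day 365 or Day 730 visit in the analysis by using the relative date. No section states an order of precedence between the two missing-baseline rules.

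**The concern.** Take two participants with the same chronic cough, sputum and wheeze on Day 1. One misses the Day 365 visit altogether, and Section 2.1 compares that person with the Day 1 values. The other attends, but the questionnaire is not completed. The visit exists, so the Section 2.1 fallback is not triggered, and Section 4.4.2.1.1 makes that person symptom-free at baseline. The participant who came to the clinic has the worse baseline information, although the Day 1 record is equally available for both.

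New onset or worsening decides who is a Case Definition 1 case. If unchanged chronic symptoms count as new, an RSV ARI that was not an LRTD by the trial's own definition becomes one. Adding such cases in both arms moves the Case Definition 1 VE toward the VE against RSV ARI in general. The situation is foreseeable: under Section 4.16, sites record reasons for ePRO assessments missing at attended visits, including the day of vaccination, and Section 5.15 repeats that analysis for Seasons 2 and 3. The SAP does not say how often this occurs.

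**Working it through.** The SAP gives no figure on this point, so there is none to reproduce.

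**1. Which rule applies when (Season 2/3 episode, earlier-season value on file)**

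| Day 365/730 situation | Section 2.1 | Section 4.4.2.1.1 | Result |
|---|---|---|---|
| Visit held, symptoms assessed | worst value at the visit | not triggered | Day 365/730 value |
| No visit of any kind | earlier-season baseline | triggered only if it overrides Section 2.1 | earlier value if read in sequence; order not stated |
| Visit held, assessment or item missing | no fallback | triggered | symptom-free, earlier value ignored |

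The third row does not depend on how the two rules are ordered.

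**2. One case.** Use the four LRTI symptoms in the RiiQ (cough, shortness of breath, sputum, wheezing; each scored 0 to 3). The earlier baseline is mild cough, sputum and wheezing: (1, 0, 1, 1). On the ARI day these are unchanged and mild shortness of breath is new: (1, 1, 1, 1).
- Against the earlier baseline, 1 symptom is above baseline. Case Definition 1 needs at least 3, so it is not met.
- Against a symptom-free baseline, 4 are above baseline, so it is met.

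**3. Direction.** A score above any baseline is also above zero, so the symptom-free rule never counts fewer symptoms. Over all 4^4 × 4^4 = 65,536 pairs of baseline and ARI-day scores:
- A score exceeds zero in 3/4 of cases. At least 3 of 4 do so in 4(0.75)³(0.25) + 0.75⁴ = 0.73828, or 48,384 pairs.
- A score exceeds its baseline in 6/16 = 0.375 of cases. At least 3 of 4 do so in 4(0.375)³(0.625) + 0.375⁴ = 0.15161, or 9,936 pairs.
- The difference is 48,384 − 9,936 = 38,448 pairs that are cases only under the symptom-free rule. There are 0 in the other direction.

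These counts are unweighted. They show direction, not prevalence.

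**4. Size.** Every input below is an assumption; none comes from the SAP.

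*Illustration A.* There are 40 placebo Case Definition 1 cases and 40 other placebo RSV ARIs. A fraction m = 2–10% lacks the baseline, and a share s = 10–30% of those has decisive chronic symptoms. VE is 70% for Case Definition 1 and 0–40% for the other ARIs. Extra placebo events = 40·m·s, and
VE = 1 − [40(0.30) + 40·m·s·(1 − VE_other)] / [40 + 40·m·s].
- Low end (m = 0.02, s = 0.10, VE_other = 0.40): 0.08 extra events; VE = 1 − 12.048/40.08 = 69.9%.
- High end (m = 0.10, s = 0.30, VE_other = 0): 1.2 extra events; VE = 1 − 13.2/41.2 = 68.0%.

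*Illustration B.* Acute onset probability per symptom is 0.50 (placebo) and 0.35 (vaccine), independent across the four symptoms. The rate ratio for any RSV ARI is 0.5. Each symptom is chronic with probability c = 10–20%, and a fraction m = 5–20% lacks the baseline. With P(p) = 4p³(1 − p) + p⁴:
- Correct baseline: P(0.50) = 0.3125, P(0.35) = 0.1265; VE = 1 − 0.5 × 0.1265/0.3125 = 79.8%.
- With a missing baseline, p becomes 1 − (1 − p)(1 − c). For c = 0.10 that is 0.55 and 0.415, giving P = 0.3910 and 0.1969. With m = 0.05, the mixed probabilities are 0.3164 and 0.1300; VE = 79.5%.
- For c = 0.20, p is 0.60 and 0.48, giving P = 0.4752 and 0.2831. With m = 0.20, the mixed probabilities are 0.3450 and 0.1578; VE = 77.1%.

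Across both illustrations the loss runs from 0.1 to 2.6 percentage points.

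**The case against.** The strongest reply is that the two sections do not contradict each other. Section 2.1 sits among the general definitions and says what the season baseline is; Section 4.4.2.1.1 then covers whatever is still missing. Section 5.4.1.1 sends the reader to Section 2.1 for exactly this purpose. A reader might infer that a participant with no Day 365 visit is given two incompatible baselines, but that follows only if Section 4.4.2.1.1 overrides the definition it relies on. The documents do not establish that, and the sequential reading is natural. This part of the objection stands. What is missing is an explicit order.

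Treating a missing baseline as normal is also a consistent convention: the same section does so for oxygen saturation and respiratory rate. Carrying an older value forward has its own error, since symptoms may have resolved in one or two years and true new onset would then be hidden. The present rule lowers VE and so does not flatter the vaccine. These points are fair and argue for a low severity. They do not explain why an earlier value is good enough for someone who missed the visit but is discarded for someone who attended.

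Finally, the missing fractions used above may be too high. Under the sequential reading only attended visits without the assessment count, and these should be rarer than all missing baselines. That also stands.

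**Conclusion.** The point holds in a narrow form. For an attended Day 365/730 visit with a missing assessment or item, the SAP ignores an available earlier-season baseline, and it does not state the order of its two missing-baseline rules. The misclassification can only add Case Definition 1 events. It is confined to the exploratory Season 2, Season 3, Seasons 2 and 3 combined, and three-season analyses. The Season 1 primary analysis and the proof-of-concept decision are not affected, because no earlier season exists there.

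The expected effect is a VE about 0 to 3 percentage points lower, with 0.1 to 1.2 extra placebo events in illustration A. Both figures rest wholly on assumed case counts, missing fractions and symptom patterns.

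Two further inferences are not supported. The SAP has no data showing that the effect concentrates in the increased-risk subgroup, and neither calculation examined it. Nor does the possibility of few RSV cases in Seasons 2 and 3 (Section 5) make the problem larger: the expected number of reclassified cases falls with the number of RSV ARIs. Severity: minor.

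**What to change.** State in Section 4.4.2.1.1 that the baseline is first selected under Section 2.1. Extend the Section 2.1 fallback to the item level: if a Day 365/730 value for a symptom or sign is missing for any reason (no visit, or a visit without that assessment or item), use the most recent earlier-season baseline for that item. Limit the symptom-free assumption to items with no earlier value.

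The cost is a few sentences of SAP text and a per-item step in the baseline derivation, using data already collected. The downside is an older baseline for a few participants, which Section 2.1 already accepts for missed visits.
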